5.11.3.2 Clarifications and Exceptions

The intervention under investigation in Prepare ABC is pre- and post-operative exercise. Surgery is conducted in all patients on the trial as part of routine care. All post-operative morbidity up to 30 days post-operation and readmissions up to 90 days are collected as primary and secondary outcome measures in all patients and are not therefore subject to routine safety reporting.

Adverse events include

- An exacerbation of a pre-existing illness
- An increase in frequency or intensity of a pre-existing episodic event or condition
- A condition (regardless of whether PRESENT prior to the start of the trial) that is DETECTED after trial exercise intervention. (This does not include pre-existing conditions recorded as such at baseline as they are not detected after exercise intervention.)
- Continuous persistent disease or a symptom present at baseline that worsens

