5.6.1.7 Surgery

Surgery and after care to follow treatment as usual, with no further study interventions until 6 weeks post-surgery. All POMs and length of hospital stay to be recorded in patient notes and ultimately captured in the eCRF.

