5.10.4.5 Analysis Population and Missing Data

The analyses population are defined as:

- a) intention-to-treat: all randomised individuals regardless of adherence;
- b) per-protocol: all randomised individuals who adhere to the study regime attending at least 50% of the hospital supervised exercise sessions or participate in at least 50% of scheduled phone calls with a member of the trial intervention team relative to the treatment arm they are allocated to.
- c) safety population:
 - Arm A all randomised individuals who receive a manual and attended a minimum of one supervised exercise session
 - Arm B all randomised individuals who receive a manual
 - Arm C all randomised individuals

Missing data that occur in outcomes will be multiply imputed to increase precision of the treatment effect estimates. Sensitivity analyses will be conducted to assess the impact of the multiple imputations and a complete case analysis will also be conducted. All imputations will be examined to ensure sensible values are being generated. Imputation models will contain baseline measures, outcome measures and factors predictive of missing data.

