5.11.3.1 Safety reporting

The principles of ICH GCP require that investigators and sponsors follow specific procedures when notifying and reporting adverse events or adverse reactions in clinical trials. These procedures are described below.

Table 2: Adverse Event Definitions

Adverse Event (AE)	Any untoward medical occurrence in a patient or clinical trial participant and which does not necessarily have a causal relationship with the trial exercise intervention.	
Adverse Reaction (AR)	Any unintended or untoward response to an investigational intervention	
Serious Adverse Event (SAE) or Serious Adverse Reaction (SAR)	 Any AE that at any dose: results in death is life threatening* requires hospitalisation or prolongs existing hospitalisation** results in persistent or significant disability or incapacity is a congenital anomaly or birth defect or is another important medical condition*** 	

^{*} the term life threatening here refers to an event in which the patient is at risk of death at the time of the event; it does not refer to an event that might hypothetically cause death if it was more severe (e.g. a silent myocardial infarction)

^{**} Hospitalisation is defined as an in-patient admission, regardless of length of stay, even if the hospitalisation is a precautionary measure for continued observation. Hospitalisation for pre-

existing conditions (including the planned surgery/elective procedures that have not worsened as a result of exercise) do not constitute an SAE

*** Medical judgement should be exercised in deciding whether an AE is serious in other situations. Important AEs that may not be immediately life threatening or result in death or hospitalisation, but may seriously jeopardise the participant by requiring intervention to prevent one of the other outcomes listed in the table (e.g. a secondary malignancy, an allergic bronchospasm requiring intensive emergency treatment, seizures or blood dyscrasias that do not require hospitalisation, or development of drug dependency).

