5.11.3.3 Exempted Adverse Events

Adverse events do NOT include

- Post-operative morbidity (within 30 days of surgery) this should be graded according to the Clavien Dindo classification and reported on the appropriate eCRF
- Readmissions relating to post-operative morbidities within 90 days of surgery
- Recurrence of primary cancer- this should be reported on the appropriate eCRF
- Death due to primary cancer- this should be reported on the appropriate eCRF
- Medical or surgical procedures; the condition that led to the procedure is the adverse event
- Pre-existing disease or a condition present that was diagnosed before trial entry and does not worsen
- Hospitalisation where no untoward or unintended response has occurred e.g. elective surgery, social admissions

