5.11.3.6.2 Causality and Expectedness

The investigator must assess the causality of all serious adverse events in relation to the exercise intervention using the definitions in Table 2. There are 5 categories: unrelated, unlikely, possible, probably and definitely related. If the causality assessment is assessed as unrelated or unlikely to be related the event is classified as an SAE. If the causality is assessed as possible, probable or definitely related then the event is classified as an SAR.

Expectedness is assessed by trained NCTU staff against a list of events produced by the co-Cls.

If the event is classified as 'serious' and assessed as being related to the exercise intervention then an SAE form must be completed and NCTU notified within 24 hours. If the event is classified as 'serious' and assessed as **not** being related to the exercise intervention or is thought to be related to a post-operative morbidity (POM) these should still be reported to NCTU via the relevant eCRF forms.

If an SAE is considered to be related to the exercise intervention then continuation of the exercise intervention should be discussed with the Chief Investigator

Table 3: Causality definitions

Relationship	Description	Event type	
Unrelated	There is no evidence of any Unrelated SAE causal relationship		
Unlikely to be related	There is little evidence to suggest that there is a causal relationship (e.g. the event did not occur within a reasonable time after administration of the trial medication). There is another reasonable explanation for the event (e.g. the participant's clinical condition or other concomitant treatment)	Unrelated SAE	
Possibly related	There is some evidence to suggest a causal relationship (e.g. because the event occurs within a reasonable time after administration of the trial medication). However, the influence of other factors may have contributed to the event (e.g. the participant's clinical	SAR	

	condition or other concomitant	
	treatment)	
Probably related	There is evidence to suggest a	SAR
	causal relationship and the	
	influence of other factors is	
	unlikely	
Definitely related	There is clear evidence to	SAR
	suggest a causal relationship	
	and other possible contributing	
	factors can be ruled out	

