5.11.3.7 Notifications

5.11.3.7.1 Notifications by the Investigator to NCTU

NCTU must be notified of all SAEs related to the exercise intervention within 24 hours of the investigator becoming aware of the event.

Investigators should record any SAEs related to the exercise intervention occurring from the time of randomisation until 12 months post-randomisation, when the exercise intervention stops.

The SAE form must be scanned and sent by email to the NCTU SAE reporting email address:

[contact]

The SAE form must be completed by the investigator (the consultant named on the delegation of responsibilities list who is responsible for the participant's care). In the absence of the responsible investigator, the SAE form should be completed and signed by a member of the site trial team and emailed as appropriate within the timeline. The responsible investigator should check the SAE form at the earliest opportunity, make any changes necessary, sign and then email to NCTU. Detailed written reports should be completed as appropriate. Systems will be in place at the site to enable the investigator to check the form for clinical accuracy as soon as possible.

The minimum criteria required for reporting an SAE are the PIN and date of birth, name of reporting investigator and sufficient information on the event to confirm seriousness. Any further information regarding the event that is unavailable at the time of the first report should be sent as soon as it becomes available.

Participants must be followed up until clinical recovery is complete and laboratory results have returned to normal or baseline values, or until the event has stabilised. Follow-up should continue after completion of protocol treatment and/or trial follow-up if necessary. Follow-up SAE forms (clearly marked as follow-up) should be completed and emailed to NCTU as further information becomes available. Additional information and/or copies of test results etc. may be provided separately. The participant must be identified by trial number, date of birth and initials only. The participant's name should not be used on any correspondence and should be blacked out and replaced with trial identifiers on any test results.

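### Sections 5.11.3.2, 5.11.3.3 and 5.11.3.7.1 conflict on readmissions to day 90, and the Arm A safety population leaves out patients who never attended a supervised session

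*Protocol*

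**What the plan says.** **Readmissions.** Section 5.11.3.2 explains that "readmissions up to 90 days are collected as primary and secondary outcome measures in all patients and are not therefore subject to routine safety reporting". The list of exempted events in section 5.11.3.3 is narrower: "Readmissions relating to post-operative morbidities within 90 days of surgery". Section 5.11.3.1 makes an event serious if it "requires hospitalisation or prolongs existing hospitalisation". Section 5.11.3.7.1 states that "NCTU must be notified of all SAEs related to the exercise intervention within 24 hours" and covers related SAEs "occurring from the time of randomisation until 12 months post-randomisation, when the exercise intervention stops". For serious events judged unrelated to exercise, or attributed to post-operative morbidity, section 5.11.3.6.2 adds that "these should still be reported to NCTU via the relevant eCRF forms". Section 5.6.1.7 places surgery and aftercare outside the intervention, "with no further study interventions until 6 weeks post-surgery".

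**Safety population.** Section 5.10.4.5 defines it separately for each arm. For Arm A it is "all randomised individuals who receive a manual and attended a minimum of one supervised exercise session". For Arm B it is those randomised who receive the manual, and for Arm C everyone randomised. Section 5.10.4.7 bases the adverse event and SAE tables on this population. Section 5.6.1.5 gives Arm A two home resistance sessions a week besides the supervised cycling, and sets no minimum number of supervised sessions.

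**The concern.** There are two separate problems.

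First, a site that readmits a patient because of trial exercise in the third month after surgery finds one section removing the event from safety reporting and another requiring notification within 24 hours. The reason given in 5.11.3.2 is that readmissions are already collected as an outcome. That outcome, in section 5.5.2, is all-cause, and no attribution to exercise is described for it. If the site treats the admission only as an outcome, the causality assessment in 5.11.3.6.2, which applies to SAEs, may never start. The event could then be absent from the exercise-related adverse events that section 5.11.3 promises to the DMC.

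Second, membership of the Arm A safety set depends on something that happens after randomisation and that harm itself could prevent. No such condition applies in Arm C, and Arm B has only the weaker condition of receiving the manual. The final safety tables would thus compare a selected Arm A group with an unselected control group.

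**Working it through.** The protocol states no figure to reproduce. The check is a comparison of sections with simple date arithmetic.

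**1. Length of the conflict on readmissions**

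- Restart of trial exercise (5.6.1.7): 6 weeks × 7 = day 42 after surgery.
- End of the readmission exemption (5.11.3.2 and 5.11.3.3): day 90.
- Overlap: 90 − 42 = 48 days, and 48 / 90 = 53% of the exempt period.

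This is a maximum per participant. Section 5.6.1.10 lets patients with complications restart later. It measures calendar time, not events.

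**2. One admission under each section**

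Take an in-patient admission between day 42 and day 90 that the investigator judges possibly, probably or definitely related to exercise and not related to post-operative morbidity.

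| Section | Result |
|---|---|
| 5.11.3.1 | Serious, because it is an in-patient admission |
| 5.11.3.2 | Outside routine safety reporting, because it is a readmission before day 90 |
| 5.11.3.3 | Not exempt, because it does not relate to post-operative morbidity |
| 5.11.3.6.2 | A serious adverse reaction; SAE form and notification within 24 hours |
| 5.11.3.7.1 | Notifiable within 24 hours; no exception for readmissions |

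Only 5.11.3.2 exempts this admission. The other sections make it reportable or leave it so.

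**3. One Arm A patient under the safety population rule**

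Take a patient randomised to Arm A who receives the manual, does home resistance exercise, is harmed and never attends a supervised session.

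- SAE notification (5.11.3.7.1): runs from randomisation whatever the attendance, so a related SAE is still notified.
- Safety population (5.10.4.5): not met, because no supervised session was attended.
- Safety tables (5.10.4.7): the patient and the event are both absent.
- The same patient in Arm B would be counted on receipt of the manual.

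**4. Number of patients affected**

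The protocol gives no rate of zero supervised attendance. As an assumption only, take the planned arm size of 1146 / 3 = 382:

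- 1% with no supervised session: 382 × 0.01 = about 4 patients excluded
- 5%: 382 × 0.05 = about 19
- 10%: 382 × 0.10 = about 38

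These are excluded patients, not lost harms. Section 5.12 suspends Arm A during the pandemic, so the actual arm may be smaller than planned.

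**The case against.** The strongest reply is that the rules taken together exempt only morbidity-related readmissions. On this view 5.11.3.2 is explanatory, 5.11.3.3 is the operative list, and 5.11.3.7.1 imposes a specific duty that should prevail. Other routes also capture events. Serious events judged unrelated or morbidity-related go to NCTU on the eCRF. Exercise adverse events continue to be recorded in both exercise arms after 6 weeks (5.6.1.10). All-cause 90-day readmission is compared between arms as a secondary outcome. The IDMC sees accumulating comparative data (5.11.4.4.4), and nothing confines that to the safety population.

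Much of this stands. A reader might infer that every readmission to day 90 is settled as exempt. The documents do not support that, because 5.11.3.3, 5.11.3.6.2 and 5.11.3.7.1 say otherwise, and a careful site would report correctly. What remains is that 5.11.3.2 gives a plain contrary instruction on a 24-hour duty.

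A reader might also infer that the Arm A rule removes events from reporting as well as from the tables. It does not, since it defines an analysis population only.

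On the safety set, a definition based on exposure is a common choice, and the protocol does not say that home resistance exercise begins before the first supervised session. That makes the excluded case less frequent but not impossible. The Arm A rule also fails as an exposure rule, because it counts only one of the two kinds of exercise that the arm prescribes.

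**Conclusion.** Both points hold, at moderate priority.

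1. The protocol contradicts itself on exercise-related readmissions for up to 48 days per exercise participant. Under-reporting follows only if a site acts on 5.11.3.2 and overlooks the other sections.
2. Followed exactly, 5.10.4.5 and 5.10.4.7 drop from the safety tables any Arm A patient with no supervised session, while Arms B and C have weaker conditions or none. This is an arm-specific selection after randomisation. It affects the tables and not SAE notification.

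The size of the second effect cannot be determined from the protocol. It would be tempting to say that one or two lost events could overturn the safety conclusion, but the protocol gives no expected number of exercise-related SAEs, so nothing supports that. The first conclusion assumes that exercise restarts at the earliest permitted time. The second assumes that some Arm A patients do home exercise without ever attending a supervised session.

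**What to change.** - **Section 5.11.3.2:** limit the exemption to readmissions relating to post-operative morbidity, matching 5.11.3.3. Add that any serious event judged possibly, probably or definitely related to exercise is notified under 5.11.3.7.1, including when it is a readmission within 90 days. Keep this to serious events: under 5.11.3.1 and 5.11.3.6.2 a serious adverse reaction is by definition serious, so wording that covered all related events would bring non-serious ones into the 24-hour route.
- **Section 5.10.4.5:** define the Arm A safety population as for Arm B, that is, all randomised patients who receive the manual.

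A separate safety table of readmissions by arm is not essential, because the secondary outcome largely covers it.

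The cost is amendment wording and a few more SAE forms from sites, with no new data collection. The Arm A safety set will include some patients with little exposure, which may slightly dilute event rates in that arm. Arm B already accepts this.

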5.11.3.3 Exempted Adverse Events

Adverse events do NOT include

- Post-operative morbidity (within 30 days of surgery) this should be graded according to the Clavien Dindo classification and reported on the appropriate eCRF
- Readmissions relating to post-operative morbidities within 90 days of surgery
- Recurrence of primary cancer- this should be reported on the appropriate eCRF
- Death due to primary cancer- this should be reported on the appropriate eCRF
- Medical or surgical procedures; the condition that led to the procedure is the adverse event
- Pre-existing disease or a condition present that was diagnosed before trial entry and does not worsen
- Hospitalisation where no untoward or unintended response has occurred e.g. elective surgery, social admissions

5.11.3.4 Other Notifiable Adverse Events

There are no further notifiable events in this trial.

5.11.3.5 Procedures to follow in the event of female participants becoming pregnant

In the event of a female participant becoming pregnant, trial intervention along with standard of care procedures should be discussed with the CIs. This should be reported on the eCRF. The pregnancy should be followed for outcome of mother and child.

5.11.3.6 Investigator responsibilities relating to safety reporting

All AEs and SAEs whether expected or not, should be recorded in the patient's medical notes and reported in the toxicity section of the relevant eCRF.

5.11.3.6.1 Seriousness assessment

When an AE occurs, the investigator responsible for the care of the participant must assess whether or not the event is serious using the definition given in Table 1.

5.11.3.6.2 Causality and Expectedness

The investigator must assess the causality of all serious adverse events in relation to the exercise intervention using the definitions in Table 2. There are 5 categories: unrelated, unlikely, possible, probably and definitely related. If the causality assessment is assessed as unrelated or unlikely to be related the event is classified as an SAE. If the causality is assessed as possible, probable or definitely related then the event is classified as an SAR.

Expectedness is assessed by trained NCTU staff against a list of events produced by the co-Cls.

If the event is classified as 'serious' and assessed as being related to the exercise intervention then an SAE form must be completed and NCTU notified within 24 hours. If the event is classified as 'serious' and assessed as **not** being related to the exercise intervention or is thought to be related to a post-operative morbidity (POM) these should still be reported to NCTU via the relevant eCRF forms.

If an SAE is considered to be related to the exercise intervention then continuation of the exercise intervention should be discussed with the Chief Investigator

Table 3: Causality definitions

Relationship	Description	Event type	
Unrelated	There is no evidence of any Unrelated SAE causal relationship		
Unlikely to be related	There is little evidence to suggest that there is a causal relationship (e.g. the event did not occur within a reasonable time after administration of the trial medication). There is another reasonable explanation for the event (e.g. the participant's clinical condition or other concomitant treatment)	Unrelated SAE	
Possibly related	There is some evidence to suggest a causal relationship (e.g. because the event occurs within a reasonable time after administration of the trial medication). However, the influence of other factors may have contributed to the event (e.g. the participant's clinical	SAR	

	condition or other concomitant	
	treatment)	
Probably related	There is evidence to suggest a	SAR
	causal relationship and the	
	influence of other factors is	
	unlikely	
Definitely related	There is clear evidence to	SAR
	suggest a causal relationship	
	and other possible contributing	
	factors can be ruled out	

5.11.3.7 Notifications

5.11.3.7.1 Notifications by the Investigator to NCTU

NCTU must be notified of all SAEs related to the exercise intervention within 24 hours of the investigator becoming aware of the event.

Investigators should record any SAEs related to the exercise intervention occurring from the time of randomisation until 12 months post-randomisation, when the exercise intervention stops.

The SAE form must be scanned and sent by email to the NCTU SAE reporting email address:

[contact]

The SAE form must be completed by the investigator (the consultant named on the delegation of responsibilities list who is responsible for the participant's care). In the absence of the responsible investigator, the SAE form should be completed and signed by a member of the site trial team and emailed as appropriate within the timeline. The responsible investigator should check the SAE form at the earliest opportunity, make any changes necessary, sign and then email to NCTU. Detailed written reports should be completed as appropriate. Systems will be in place at the site to enable the investigator to check the form for clinical accuracy as soon as possible.

The minimum criteria required for reporting an SAE are the PIN and date of birth, name of reporting investigator and sufficient information on the event to confirm seriousness. Any further information regarding the event that is unavailable at the time of the first report should be sent as soon as it becomes available.

Participants must be followed up until clinical recovery is complete and laboratory results have returned to normal or baseline values, or until the event has stabilised. Follow-up should continue after completion of protocol treatment and/or trial follow-up if necessary. Follow-up SAE forms (clearly marked as follow-up) should be completed and emailed to NCTU as further information becomes available. Additional information and/or copies of test results etc. may be provided separately. The participant must be identified by trial number, date of birth and initials only. The participant's name should not be used on any correspondence and should be blacked out and replaced with trial identifiers on any test results.

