5.4 Interventions

There are three trial arms:

- Arm A Hospital based supervised exercise
- Arm B Home based supported exercise
- Arm C Standard care, treatment as usual

Patients undergoing curative surgery for colorectal cancer are not routinely investigated with a CPET to assess cardiopulmonary fitness, or given any advice/support with respect to exercise prior to surgery.

All patients, once consented to the trial, will have a baseline CPET and another CPET immediately prior (within 7 days) of their planned colorectal surgery.

Data on planned type of surgery (laparoscopic or open) and tumour histological stage data at 30 days post-surgery will be collected and recorded on the relevant pages of the eCRF. If a patient is found to have had a benign tumour post-operatively, they may continue to participate in the study as per protocol.

If the patient is undergoing rectal cancer long course chemo-radiotherapy, this should be carried out before the patient is consented to the trial. There would then be a 6 week delay to their participation whilst they undergo chemo-radiotherapy. Once chemo-radiotherapy is complete, the patient will be approached for informed consent and a baseline assessments performed.

Patients will then receive, in addition to treatment as usual, the interventions below, depending on their treatment arm allocation during randomisation.

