5.4.3 Arm C - Standard Care, Treatment as Usual

Apart from two pre-surgery CPETs, patients randomised to the control arm of the study will follow the current standard care pathway – no further information or advice will be offered with respect to pre- or post-operative exercise outside of standard care for the Trust.

As part of the process evaluation, an assessment of current practice will be performed.

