5.6.1.2 Baseline visit

Once the participant has given written informed consent, an initial CPET* should be performed.

If the participant is undergoing rectal cancer long course chemo-radiotherapy, this should be carried out before the baseline assessments.

All participants should have the following questions/questionnaires asked/administered; Quality of Life Questionnaires SF36 and EQ-5D-5L, Behavioural Regulation in Exercise Questionnaire (BREQ-3), Exercise Identity Scale (EIS), The Hospital Anxiety and Depression Scale, Self -Efficacy for Exercise Scale, modified version of Godin Leisure Time Exercise Questionnaire and Resource Use Questionnaire. Grip Strength should be measured using a standard digital grip strength dynamometer.

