5.6.1.4 CPET guidance

For the purposes of this study, cardiopulmonary exercise tests should be completed as per standard local processes and procedures. However, the results should be uploaded onto the eCRF in breath-by-breath and/or 30 second average formats where possible.

If CPETs are carried out as part of standard care pre-surgical assessments, the results may be used for the baseline time point provided they are within 28 days of randomisation.

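### A serious event caused by a trial-mandated CPET has no relatedness category and no expedited route, and the start of SAE recording for the baseline CPET is not stated

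*Protocol*

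**What the plan says.** **The tests.** Protocol section 5.4 states that these patients "are not routinely investigated with a CPET to assess cardiopulmonary fitness". It then requires the test twice: "All patients, once consented to the trial, will have a baseline CPET and another CPET immediately prior (within 7 days" of surgery). Section 5.6.1.2 places the first test after consent: "Once the participant has given written informed consent, an initial CPET* should be performed". Section 5.9.1 puts randomisation after it. Section 5.4.3 confirms that controls have both: "Apart from two pre-surgery CPETs, patients randomised to the control arm of the study will follow the current standard care pathway". Section 5.5.2 has the CPET variables determined at maximum exercise tolerance.

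**Exceptions.** Section 5.6.1.3 allows randomisation without CPET data in exceptional circumstances, with a late baseline test within 7 days afterwards if feasible. Section 5.6.1.6 allows the second test to be missed. Section 5.6.1.4 allows a routine test to be reused: "If CPETs are carried out as part of standard care pre-surgical assessments, the results may be used for the baseline time point", if it was done within 28 days of randomisation.

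**Safety reporting.** Section 5.11.3.6.2 says "The investigator must assess the causality of all serious adverse events in relation to the exercise intervention". The SAE form and the 24-hour notice apply to serious events judged related to that intervention (5.11.3.6.2, 5.11.3.7.1). The recording period for these is given as "Investigators should record any SAEs related to the exercise intervention occurring from the time of randomisation until 12 months post-randomisation". Section 5.11.3.7.2 gives NCTU the task of reporting intervention-related SAEs to the REC. Separately, section 5.11.3.6 requires every AE and SAE to go into the notes and the eCRF, and section 5.11.3.6.2 sends serious events not related to exercise to NCTU through eCRF forms. Section 5.11.3.7.2 provides for medical review of the SAE reports that NCTU receives.

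**The concern.** Apart from routine tests that are reused, the CPETs are done because of the trial, and they are the main physical exertion that it asks of control patients. Eligibility extends to ASA III (5.3.1.1) and to patients with stable previous cardiovascular conditions (5.3.1.2). A reporting system for trial-caused harm should be able to label harm from the trial's own procedures as related and to act on it quickly. Here relatedness has a single reference point, the exercise intervention. If CPET lies outside it, the trial could report no related SAEs, correctly under its own definitions, although one of its procedures had caused some. The sponsor and the REC would have no prompt notice on which to act.

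**Working it through.** No arithmetic applies, and there is no protocol figure to reproduce. The check sets the sections side by side.

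**Step 1. Is CPET a trial procedure?** Yes, in general. Section 5.4 says it is not routine and requires it, section 5.4.3 extends it to controls, and sections 5.6.1.2 and 5.6.1.6 schedule it. A standard-care test reused under 5.6.1.4 is the exception, and some tests will be waived.

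**Step 2. Could CPET count as part of the exercise intervention?** The text separates them. Section 5.6.1.3 permits a late baseline CPET provided that it comes before the exercise intervention starts. Section 5.4 describes the interventions as what follows baseline assessment, according to allocation. Arm C has two CPETs and no exercise intervention.

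**Step 3. What depends on relatedness to exercise?** The SAE form, the 24-hour notice and REC reporting all do. Table 3 offers no category for a trial procedure, and its examples refer to a medication, which this trial does not give.

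**Step 4. Trace a serious event caused by a CPET.**

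| Case | Can it be classed as related? | 24-hour notice | What remains |
|---|---|---|---|
| Baseline CPET before randomisation | No: no intervention has started | None; the stated period starts at randomisation and covers exercise-related SAEs only | Notes and eCRF under 5.11.3.6, which gives no start date |
| CPET after randomisation, Arm A or B | Only if exercise training is also thought to have contributed; not if CPET alone was the cause | Only in that event | eCRF to NCTU, no deadline |
| CPET after randomisation, Arm C | No: no exercise intervention exists | Cannot be triggered | eCRF to NCTU, no deadline |

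**Step 5. Does the remaining route lead to medical review?** Section 5.11.3.7.2 covers SAE reports received and has no relatedness condition. Non-related serious events, however, arrive through eCRF forms and not the SAE form. The protocol does not say whether an eCRF entry counts as an SAE report. Review is therefore neither excluded nor assured, and no time limit applies to it.

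**The case against.** The strongest reply is that nothing is lost. Section 5.11.3.6 covers all AEs and SAEs, with no window and no relatedness condition. The AE definition in 5.11.3.1 needs no causal link to exercise, so a CPET event qualifies. Section 5.11.3.6.2 names NCTU as recipient of serious events not related to exercise. Section 5.10.4.7 tabulates AEs and SAEs without restriction to related ones, and the Arm C safety population is everyone randomised to it. Section 5.11.3 gives the data monitoring committee safety data by arm that include, but are not confined to, exercise-related events. Patients with contraindications to exercise are excluded, and Trust staff perform the tests under local procedures.

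Most of this stands, and it rules out several stronger readings that a reader might infer:

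- **That CPET-caused events escape central review.** They should reach NCTU by eCRF. What is missing is a deadline and a statement that such entries are medically reviewed.
- **That a baseline CPET event is barred from recording.** The randomisation start governs exercise-related SAEs only. For other events the start is unstated.
- **That the committee would miss a cluster.** Its terms of reference are a separate document that is not available here.
- **That the planned number of CPETs measures the problem.** Tests may be waived, reused from standard care or done late. The suspension of Arm A in 5.12 changes the split between arms. The sample size counts randomised patients, whereas the baseline test follows consent. A count of tests also says nothing about how often harm occurs.

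The reply does not answer the core. Being recorded on an eCRF is not the same as being classed as related, notified within 24 hours and reported to the REC.

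**Conclusion.** The concern holds in a limited form. A serious event caused by a trial-mandated CPET has no relatedness category, no expedited route and no stated REC route. In Arm C the 24-hour trigger cannot be met at all. Medical review of such an event is possible but untimed and not assured. For a baseline CPET done before randomisation, the start of SAE recording is not stated.

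The conclusion rests on reading CPET as separate from the exercise intervention, which sections 5.4, 5.4.3 and 5.6.1.3 support. The protocol gives no CPET event rate, so no number of affected participants can be derived. No sample size, power, significance level or primary analysis is touched. Because serious events do have a written path to NCTU, this is a gap in classification and timing that should be fixed, not a failure of safety recording as a whole.

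**What to change.** - **5.11.3.6.2 and Table 3:** assess causality in all arms against the exercise intervention or a trial-mandated CPET, and replace the references to trial medication.
- **5.11.3.7.1:** extend the SAE form and the 24-hour notice to CPET-related SAEs, with recording from consent, so that the baseline test is covered.
- **5.11.3.7.2:** include CPET-related SAEs in medical review and in REC reporting, and state whether serious events entered only on the eCRF also receive medical review.
- **5.11.3.6:** reconcile the general recording rule with the sections above, so that start of recording, route and deadline agree.

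The cost is a wording amendment with a matching change to the SAE form, and a few more expedited reports. No extra visits or assessments are needed.
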